# 3. List of Abbreviations

AE Adverse Event

AID Absolute Iron Deficiency

CAA Cancer Associated Anemia

CIOMS Council for International Organizations of Medical Sciences

CRF Case report form

CRP C-Reactive Protein

ECOG Eastern Cooperative Oncology Group

ESA Erythropoiesis-Stimulating Agents

FCM Ferric Carboxymaltose

FID Functional Iron Deficiency

Hb Hemoglobin

ICH International Conference on Harmonization

IDA Iron Deficiency Anemia

IRB Institutional Review Board

JFDA Jordan Food and Drug Administration

KHCC King Hussein Cancer Center

QOL Quality of Life

Rx History Drug History

SAE Serious Adverse Event

TIBC Total Iron Binding Capacity

TSAT Transferrin Saturation

US FDA the United States Food and Drug Administration

WMA World Medical Association

#### **INCLUSION CRITERIA** Patient is an adult $\geq$ 18 years old at the time of informed consent. Patient has pathologic diagnosis of solid tumor (breast cancer, colorectal, lung, sarcoma, head & neck, sarcoma, genitourinary or gynecological cancer). Patients who started chemotherapy (with or without radiotherapy) or planned to receive chemotherapy for at least 12 weeks. Patient has an Eastern Cooperative Oncology Group (ECOG) performance status between 0 and 2. Patient with Hb ≤11 g/dL. Patient has a Life expectancy at least 6 months. Adequate hepatic & renal function defined as a serum aspartate aminotransferase or alanine aminotransferase level that are no more than 3 times the upper limit of the normal range, a serum bilirubin level that is no more than 2 times the upper limit of the normal range and a serum Creatinine level of less than 2 mg per deciliter. Patient is able to understand and provide informed consent to participate in the study. **EXCLUSION CRITERIA** Patient has Hb < 8.0 g/dL Patient presenting with hematologic malignancy including any of the following: Acute Leukemia, MDS (Myelodysplastic Syndromes), CML, CLL, Multiple Myeloma, Myelodysplastic syndrome and lymphoma with bone marrow involvement Prior gastric surgery. Patients on definitive radiotherapy alone. Patients with relevant history (within six weeks) or clinical evidence of hemolysis or active bleeding that could, in the investigator's judgment, be a potential cause for the anemia (no gross hematuria, hemoptysis, hematochezia or melena and negative stool for hemoccult-at least one reading) Presence of other nutritional anemia; deficiency of vitamin B12<187pg/ml and deficiency of Folate<3.1ng/ml according to the local laboratory normal ranges. Patient has Iron overload (Serum Ferritin > 800 ng/ml or Transferrin saturation (TSAT) > 40%) Patient is pregnant or lactating. Patient has a personal or family history of hemochromatosis. Patient has hypersensitivity to any form of IV iron. Patient has received red blood cells (RBCs) transfusion or used erythropoietin within 2 weeks of enrollment into the study. Patient has received any form of IV iron within the last 12 weeks Patient has received oral iron supplements within 1 month of enrollment to the study, except for multivitamin supplements containing less than 30mg iron. Hb at baseline and at 3,6,9 and 12 weeks **EFFICACY ASSESSMENTS**

| OTHER ASSESSMENTS         | 
 
Serum ferritin level (baseline and at 12 weeks)
 
Liver Enzymes (ALT, AST), Alk Phosphatase, GGT, LDH and serum phosphate levels at base line and at week-3
 
Record all adverse events
 
CRP levels at baseline
 
Hepcidin at baseline
 
   |
|---------------------------|---|
| STUDY SITE                | King Hussein Cancer Center (KHCC)   |
| ETHICAL
CONSIDERATIONS | 
 
The study will be submitted for ethical review and approval before execution.
 
Informed consent will be obtained from study patients before implementing any study procedure.
 
   |
| STATISTICAL PLAN          | Descriptive statistics will be used to present the two groups baseline characteristics and disease information.  Analysis will be done for the two groups separately:  Group I: Patient Iron-deficiency anemia based on iron studies at base line Group II: Patient with non-iron deficiency anemia  Hb test results will be presented as mean, median and range through all twelve weeks.  Average percent change from baseline will be used to show the changes of Hb level. Comparison between means of Hb level will be made between the baseline Hb and Hb levels in the following weeks using Paired T-test.  Response to IV iron therapy will be assessed in relation to Hepcidin and CRP levels.  Univariate analysis will be used to assess the effect of patient characteristics and disease variables on the response using Chi square test or fisher's exact test.  Adjusting for all significant factors that may affect the response will be done using Logistic regression.  Odds ratio out of the Logistic regression will be reported with their corresponding 95% CI.  A significance criterion of p< 0.05 will be used in the analysis.  All analyses will be performed using SAS version 9.4 (SAS Institute Inc, Cary, NC). |

## 5. Introduction

#### 5.1 Background

Anemia, defined as an inadequate circulating level of hemoglobin, is a common complication of cancer and its treatment; especially in patients undergoing chemotherapy and/or radiotherapy. It may arise from the underlying disease, bleeding, poor nutrition, chemotherapy, or radiation therapy. Prevalence of anemia varies between 30 and 60 %. Preliminary studies suggest that survival and loco-regional control after radiation therapy, especially in head and neck and cervical cancers, may be compromised by anemia.

Anemia often worsens symptoms such as fatigue, weakness, and dyspnea, and thus may have a negative impact on the quality of life (QOL) and performance status of patients with cancer. Thus, to improve physical functioning, QOL, and prognosis in patients with cancer, it would be reasonable to take a proactive approach in identifying populations who need treatment for cancer-associated anemia (CAA) and provide a timely management.

#### **5.1.1 Transfusions**

Blood transfusion is an effective way to replace depleted Hb within a short period, but the effect is, unfortunately, temporary and can cause serious adverse risks and increase mortality.

#### 5.1.2 Erythropoiesis-stimulating agents (ESAs)

ESAs were proposed as an effective treatment for anemia for several years. Randomized clinical trials in patients with CAA has demonstrated that ESAs produced significant increases in Hb level, decreased transfusion requirements, and improved QOL. However, 30%-50% of patients do not respond to such agents. Lack of response to erythropoietin stimulation in patients with cancer is partly attributed to the functional iron deficiency state, in which the high rate of erythropoiesis exceeds the delivery of usable iron, despite adequate iron stores. Many randomized trials were conducted to examine the role of IV iron in addition to ESAs in the treatment of anemia in patients with cancer. Many of these studies showed improvement in ESA response, time to maximal response, reduction in ESA dose, and improvement in QOL parameters, when measured, in favor of the combination over ESAs alone. The observed benefit was independent of baseline iron parameters.

Several recent studies had raised serious concerns related to shortened overall survival, or time to tumor progression in patients treated with ESAs especially among patients whose Hb reached levels PRT-INM-0615/09 V06

beyond 12 g/dL. These concerns, in addition to higher incidence of thromboembolism, resulted in a significant decline in the use of these agents especially among potentially curable cancers. In 2008, Centers for Medicare and Medicaid Services recommended through new guidelines that ESAs are not to be used in patients with long life expectancy.

#### **5.1.3** Parenteral Iron

Iron plays an important role in hemoglobin synthesis and an inadequate supply is a major element in the pathogenesis of anemia. Intravenous iron therapy is routinely used to treat iron-deficiency anemia especially so in patients with severe anemia and in those who failed or could not tolerate oral formulations. Absolute iron deficiency (AID) occurs when iron delivery is impaired because iron stores are depleted (serum ferritin < 100 ng/mL; transferrin saturation (TSAT) < 20%).

Functional iron deficiency (FID), on the other hand, occurs when access to iron stores is restricted or too slow to keep-up with the process of erythropoiesis. In cancer, tumor cells interact with the immune system leading to a chronic state of inflammation. Pro-inflammatory cytokines are released leading also to the release of Hepcidin; a small (25 amino acids) peptide produced by the liver. Hepcidin is a regulator in iron homeostasis. It binds to ferroportin-expressing cells, inhibiting iron transport across cell membranes and decreasing accessibility to the iron stores. At high enough circulating levels, it impairs gastrointestinal absorption of dietary iron. This state of blocked release from stores and inhibited absorption leads to an increased frequency of iron-restricted erythropoiesis. Hence, it was proposed that patients identified with FID may benefit from the extra doses of iron to overcome the negative effect of Hepcidin.

#### 5.2 Aim of Study

In a previous pilot study conducted by our group, we investigated the use of IV iron without ESAs in a group of non-iron deficient anemic cancer patients undergoing chemotherapy. Patients were given 12 weekly short infusions of ferric sucrose while on chemotherapy. The mean increment in hemoglobin level for the 15 patients who completed at least 9 treatments was 1.7 g/dL (median, 1.1 g/dL; range, -1.9 g/dL to 3.2 g/dL). Five (20.0%) patients were transfused and considered as treatment failures. No treatment-related adverse events were reported.

With such results and to move forward with the investigation, we have considered using a new intravenous iron formulation. Ferric carboxymaltose (FCM), is widely used to treat iron deficiency anemia in different clinical settings including pregnancy-related and in chronic renal failure patients..

Therefore, the study aims to investigate the effect of FCM without ESAs on anemic cancer patients undergoing chemotherapy or radiotherapy; stratified by status of iron deficiency (i.e. non-iron deficient vs. iron deficient patients).

Furthermore, we aim to investigate the value of Hepcidin and also CRP (which is closely associated with inflammatory cytokines, as well) as predictors of response.

# 6. Study Objectives

#### **6.1 Primary objectives:**

• Assess the response to FCM in each strata

#### **6.2 Secondary Objectives:**

- Assess the utility of hepcidin and CRP in predicting response to FCM
- Assess the effect of FCM on the need for blood transfusions
- Assess the effect of FCM on the need for ESAs

#### **6.3 Study Endpoints**

#### **6.3.1 Primary Endpoint:**

- Response Rate: Percentage of patients with Hb increment of at least 1.0 gm/dL.
- Proportion of patients achieving correction of anemia (Hb >11.0 gm/dL)
- The mean Hb change from baseline to week 12

#### **6.3.2 Secondary Endpoints:**

- Response in relation to Hepcidin level.
- Response in relation to CRP level.
- Response in relation to base line iron deficiency status; iron-deficient or not.
- Parentage of patients who will require blood transfusion or ESA treatment

### 7. Rationale

Unresolved anemia is a problem in cancer patients. If it remains uncorrected, it will negatively impact patient response to treatment and QOL. With the limitations set on use of ESAs in cancer and absence of alternatives that lower the need for transfusion, iron loading is a tempting choice to explore. Trials on the use of iron as a lone treatment are generally few. This study is important in that it allows assessing FCM in both AID and FID. It will shed light on a different dosing regimen and help build understanding on the use of Hepcidin and CRP as predictors of response.

#### 7.1 Dose Rationale

Ferric carboxymaltose in a single dose, or two, is assumed sufficient to produce a clinically observable change in the status of hemoglobin in 12 weeks' time comparable to what has been achieved with small frequent doses. This has been demonstrated before using FCM in FID and lymphoid malignancies patients. FCM iron complex allows rapid increase in iron levels peaking within approximately an hour. Total serum iron levels then rapidly decline reaching normal levels within 24 to 72 hr after infusion. This allows sufficient amount of time for the body to engage the circulating iron in erythropoiesis and hence induce the proposed response. Though single high FCM dose is expected to be safe and tolerable, dosing of patients will be based on body weight to lower any chances of unwanted risks.

## 8. Patient Selection

#### 8.1 Source Population and Sample size

The study aims to enroll anemic cancer patients planned to receive chemotherapy or radiotherapy. The study sample will be selected to fulfill the selection criteria. The patient is eligible if he meets all the inclusion criteria and none of the exclusion criteria. The estimated sample size necessary in each strata is 50 which can be easily recruited in 10 months.

#### **8.2 Eligibility Criteria**

Evaluation of eligibility is the sole responsibility of the PI and will be documented in the patient CRF. If deviations from selection criteria occur, the PI will provide the proper justifications for continued inclusion of the patient in the study which will be documented in the CRF.

#### 8.2.1 Inclusion Criteria

- Patient is an adult ≥ 18 years old at the time of informed consent.
- Patient has pathologic diagnosis of solid tumor (breast cancer, colorectal, lung, sarcoma, head & neck, sarcoma, genitourinary or gynecological cancer).
- Patients who started chemotherapy (with or without radiotherapy) or planned to receive chemotherapy for at least 12 weeks.
- Patient has an Eastern Cooperative Oncology Group (ECOG) performance status between 0 and 2.
- Patient with Hb ≤11 g/dL.
- Patient has a Life expectancy at least 6 months.
- Adequate hepatic & renal function defined as a serum aspartate aminotransferase or alanine aminotransferase level that are no more than 3 times the upper limit of the normal range, a serum bilirubin level that is no more than 2 times the upper limit of the normal range and a serum Creatinine level of less than 2 mg per deciliter.
- Patient is able to understand and provide informed consent to participate in the study.

#### 8.2.2 Exclusion Criteria

Patient has Hb ≤ 8.0 g/dL

- Patient presenting with hematologic malignancy including any of the following: Acute Leukemia, MDS, CML, CLL, Multiple Myeloma, Myelodysplastic syndrome and lymphoma with bone marrow involvement
- Prior gastric surgery.
- Patients on definitive radiotherapy alone.
- Patients with relevant history (within six weeks) or clinical evidence of hemolysis or active bleeding that could, in the investigator's judgment, be a potential cause for the anemia (no gross hematuria, hemoptysis, hematochezia or melena and negative stool for hemoccult-at least one reading)
- Presence of other nutritional anemia; deficiency of vitamin B12 <187 pg/ml and deficiency of Folate < 3.1 ng/ml according to the local laboratory normal ranges

- Patient has Iron overload (Serum Ferritin > 800 ng/ml or Transferrin saturation (TSAT) > 40%)
- Patient is pregnant or lactating.
- Patient has a personal or family history of hemochromatosis.
- Patient has hypersensitivity to any form of IV iron.
- Patient has received red blood cells (RBCs) transfusion or used erythropoietin within 2 weeks of enrollment into the study.
- Patient has received any form of IV iron within the last 12 weeks
- Patient has received oral iron supplements within 1 month of enrollment to the study, except for multivitamin supplements containing less than 30mg iron.

#### 8.3 Subject Withdrawal

Patients are free to withdraw from the study at any time without prejudice or loss of benefits to which they are otherwise entitled. The investigator may remove a patient from the study if, at his discretion, the participation is seen to jeopardize the patient safety or for administrative or behavioral reasons. Neither the investigator nor the study supporting staff will try to coerce patients to continue participating in the study against their will. The withdrawal case with reasons will be documented. Withdrawn subjects will be replaced to have a complete set of 50 analyzable subjects in each strata.

Additionally, patient will be dropped out and will be considered treatment failure if

- 1 .Receive ESA or blood transfusion for medical reasons not related to the study
- 2. if they Develop a grade IV toxicity of any kind in the week between the initial and the remaining dose that is possibly related to study drug.

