### 13. Statistical Considerations

#### **13.1 Sample Size Calculation**

Patients will be recruited over a whole year tentatively between February and December, 2016. It is estimated that 2-5 % of encountered patients are anemic and eligible for enrollment.

Assuming at 90 % power, 5 % level of significance, based on previous pilot study: a proportion of responders of 0.54 and a standard deviation of 1.21, a response rate of 50 % or more being clinically meaningful, and testing for superiority; a minim of 25 subjects are required. To account for a 10 % chance for drop-outs the required sample is adjusted to 47.5 and approximated to the nearest tens. A total of fifty subjects will be required for the assessment. Since, each strata will be analyzed separately, and assuming both follow the same assumptions 50 subjects per strata will be recruited to make a total study sample of one hundred..

Recruitment of 100 patients in 10 months is doable.

East 6.3 software was used in the estimation of sample size.

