Official title:

The use of intravenous ferric carboxymaltose (FCM) without erythropoiesis-stimulating agents (ESA) in the treatment of anemia in cancer patients undergoing chemotherapy with or without radiotherapy

NCT number:

NCT04246021

Document date:

September 26, 2019

Statistical Considerations

Sample Size Calculation

Patients will be recruited over a whole year tentatively between February and December, 2016. It is estimated that 2-5 % of encountered patients are anemic and eligible for enrollment.

Assuming at 90 % power, 5 % level of significance, based on previous pilot study: a proportion of responders of 0.54 and a standard deviation of 1.21, a response rate of 50 % or more being clinically meaningful, and testing for superiority; a minim of 25 subjects are required. To account for a 10 % chance for drop-outs the required sample is adjusted to 47.5 and approximated to the nearest tens. A total of fifty subjects will be required for the assessment. Since, each strata will be analyzed separately, and assuming both follow the same assumptions 50 subjects per strata will be recruited to make a total study sample of one hundred.^{1,11}

Recruitment of 100 patients in 10 months is doable.

East 6.3 software was used in the estimation of sample size.

Statistical Analysis for data presentation

Descriptive statistics will be used to present the two groups baseline characteristics and disease information. in addition to the patient's responses after the whole follow up period.

- Analysis will be done for the two groups separately:
 - o **Group I**: Patient with iron-deficiency anemia based on iron studies at base line
 - o **Group II**: Patient with non-iron deficiency anemia
- Hb test results will be presented as mean, median and range through all twelve weeks.
- Average percent change from baseline will be used to show the changes of Hb levels.
 Comparison between means of Hb level will be made between the baseline Hb and Hb levels in the following weeks using Paired T-test.
- Response to IV iron therapy will be assessed in relation to Hepcidin and CRP levels.
- Univariate analysis will be used to assess the effect of patient characteristics and disease information on the response using Chi square test or fisher's exact test.
- Adjusting for all significant factors that may affect the response will be done using Logistic regression.
- Odds ratio out of the Logistic regression will be reported with their corresponding 95% Cl.

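### Replacing withdrawn patients up to 50 *analyzable* per stratum contradicts the planned enrolment, no all-treated efficacy set is defined, and the mean Hb change rests on patients with a week-12 Hb

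*Protocol*

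**What the plan says.** Section 8.3 lets patients withdraw freely and lets the investigator remove them for safety, administrative or behavioural reasons. It then states: "Withdrawn subjects will be replaced to have a complete set of 50 analyzable subjects in each strata". A separate rule follows. A "patient will be dropped out and will be considered treatment failure if" either of two conditions is met. One is "Receive ESA or blood transfusion for medical reasons not related to the study". The other is a possibly drug-related grade IV toxicity between the two doses. The text does not say whether these failures are also replaced.

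Elsewhere 50 is the number enrolled. Section 8.1: "The estimated sample size necessary in each strata is 50 which can be easily recruited in 10 months". Section 13.1, repeated in the SAP: "To account for a 10 % chance for drop-outs the required sample is adjusted to 47.5 and approximated to the nearest tens", and then "50 subjects per strata will be recruited to make a total study sample of one hundred".

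One of the three primary endpoints (section 6.3.1) is "The mean Hb change from baseline to week 12". The planned analysis in the SAP and in section 13.2 is: "Comparison between means of Hb level will be made between the baseline Hb and Hb levels in the following weeks using Paired T-test". Neither document gives an efficacy analysis set, a denominator for the two binary primary endpoints or a rule for missing Hb.

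**The concern.** Three gaps meet here.

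- **Two meanings of 50.** In sections 8.1 and 13.1 it is the intake, and losses come out of it. In section 8.3 it is what remains after losses have been made good. Both cannot hold.
- **No all-treated efficacy result.** Patients who withdraw, including those removed for safety, can leave the efficacy data and be replaced, and no planned analysis shows the result with them included.
- **Mean Hb change.** A treatment failure can be scored as a non-response, but the label supplies no Hb value. A paired test at week 12 uses only patients with both measurements. Transfusion and ESA are treatments for anemia, so leaving by that route is plausibly linked to low Hb. With a single arm, no control group offsets the selection.

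**Working it through.** **1. The plan's own number.** Section 13.1 starts from 25 and reaches 47.5 after a 10% allowance. That step does not reproduce: 25/0.9 = 27.8. This is a separate problem. What matters here is that the text presents 50 as rounded up from a figure already adjusted for drop-out, and as the number recruited.

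**2. Enrolment implied by section 8.3.** Patients needed = analyzable/(1 − drop-out) = 50/0.9 = 55.6, so 56 per stratum and 2 × 56 = 112 in all. The stated total is 100. Conversely, 50 recruited at 10% loss leaves 50 × 0.9 = 45.

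**3. Is an Hb obtained after drop-out?** Section 10.3 and Table 1 schedule Hb at weeks 3, 6, 9 and 12. Section 11.2 follows a discontinued patient for the adverse event. Section 16.7 promises appropriate follow-up before files are closed. None of these calls for an Hb after drop-out.

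**4. Bias in the mean among those with a week-12 Hb.** Inputs: 10% loss (section 13.1); SD 1.21 (section 13.1, which does not label it as the SD of Hb change, so this use is assumed); true mean change 0 (assumed); correlation ρ between drop-out tendency and poor Hb change (assumed, not in the documents).

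Bias = SD × ρ × φ(z)/(1 − d). With d = 0.10, z = −1.282 and φ(z) = 0.1755.

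- ρ = 0: 0
- ρ = 0.5: 1.21 × 0.5 × 0.1755/0.9 = 0.118 g/dL
- ρ = 0.7: 1.21 × 0.7 × 0.1755/0.9 = 0.165 g/dL

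The formula has no term for replacement, so the bias is the same with or without it. A different mechanism, drop-out after a low Hb already observed at a visit, gave a smaller bias in simulation: 0.08 to 0.13 g/dL at 10% loss.

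**5. False-positive rate**, two-sided p < 0.05, 200,000 simulated trials:

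| ρ | 50 treated, not replaced | Replaced to 50 with a week-12 Hb |
|---|---|---|
| 0 | about 5% | about 5% |
| 0.5 | 10.1% | 10.7% |
| 0.7 | 15.7% | 17.1% |

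Replacement raises the rate slightly only because the same bias is set against a smaller standard error: 1.21/√50 = 0.171 against 1.21/√45 = 0.180.

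**6. Response rate.** If 10% are replaced, the true rate is 50% and a proportion q of the replaced would respond, the rate shown is (0.50 − 0.1q)/0.9. For q = 0.50 it is 50.0%, for q = 0.25 it is 52.8%, and for q = 0 it is 55.6%. The values of q and the 10% replaced are illustrations.

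**7. Would a mixed model help?** In 3,000 simulated trials with 50 treated, four visits and 10% loss, it came within 0.01 g/dL of zero when drop-out followed an observed low Hb. When the low Hb behind the drop-out was not recorded, the model on scheduled values still showed +0.10 to +0.12. Recording that value brought it within 0.01 of zero when it was taken at a visit. When it was taken between visits and entered at the next visit, the result was −0.03 to −0.08. The correction is therefore approximate.

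**The case against.** **Replacement does not cause the bias in the mean.** A reader might infer from section 8.3 that it does, and that deleting the sentence would cure it. The working shows otherwise: the bias comes from the paired t-test on available week-12 values and the absence of a missing-data rule. This objection stands in full. Replacement is a problem for the enrolment conflict, for who is visible in the efficacy result, and possibly for the response rate.

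**The failure rule protects the response rate.** Largely so. The natural reading is that transfused, ESA-treated and grade IV patients stay in as non-responders, and only voluntary and investigator withdrawals are replaced. A reader might infer that failures are replaced too and that the response rate is inflated to 55.6%. The text does not say that, and the figure needs 10% of patients to be replaced with none of them responding. Inflation occurs only if replaced patients respond less often than the rest.

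**The pilot proves the pattern.** This is tempting: five transfused at 20.0% implies 25 patients, and the 1.7 g/dL increment in section 5.2 is for 15 of them. But those 15 were chosen by having completed at least nine treatments, which is an exposure cut-off and not availability of a week-12 Hb. With one or two FCM infusions, that attrition need not recur.

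**The bias is assumed and modest.** True. Correlation, SD of change and no true effect are all assumptions, and 0.12 to 0.17 g/dL is 7 to 10% of 1.7 g/dL. The enrolment conflict and the missing definitions need no assumption.

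**Safety reporting is unaffected.** Correct. The adverse-event, transfusion and ESA reporting in section 13.3 is not restricted to the analyzable set. The gap concerns efficacy.

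**Conclusion.** The concern holds, and it should be fixed. Three parts are certain from the text: *analyzable* is undefined; section 8.3 cannot be reconciled with sections 8.1 and 13.1 (about 112 patients against 100 at the plan's own drop-out rate); and there is neither an all-treated efficacy analysis nor a missing-Hb rule. It follows that the week-12 mean change, as planned, is computed on patients who still have a week-12 Hb.

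The size of the resulting bias is conditional: about 0.12 to 0.17 g/dL and a false-positive rate of about 10 to 17% at 10% loss, under the assumed SD, null effect and correlations of 0.5 to 0.7, and nothing at correlation 0. The documents do not show that drop-out will in fact follow falling Hb, nor that the response rate will be inflated. They leave both possible and plan no analysis that would reveal either.

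**What to change.** 1. Delete the replacement sentence in section 8.3 and keep enrolment at 50 per stratum.
2. Define the primary efficacy set, per stratum, as all patients who received at least one FCM infusion.
3. For both binary primary endpoints (Hb rise of at least 1.0 g/dL; Hb above 11 g/dL), state the time point of assessment. Count treatment failures and patients without an Hb at that time as non-responders in the denominator.
4. For mean change, use a repeated-measures mixed model on baseline and weeks 3, 6, 9 and 12 in all treated patients, excluding Hb after transfusion or ESA. Record the Hb that prompted a transfusion or ESA, where one was measured, and include it: the model removes the bias only when drop-out depends on an observed Hb, and even then approximately.
5. Add one pessimistic sensitivity analysis for patients without a week-12 Hb, with any penalty stated as an assumption. Show the paired t-test on available week-12 values as supportive.
6. Reconcile the restriction in section 8.3 to reasons unrelated to the study with the secondary endpoint of patients requiring transfusion or ESA.

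**Cost.** Protocol and SAP wording and one case report form field, with no extra study blood draws. Reported response rates will be less favourable, and counting missing Hb as non-response is conservative for patients who leave for administrative reasons. Intervals for mean change widen slightly. For the paired t-interval the 95% half-width is t × 1.21/√n: 0.34 g/dL at n = 50 and 0.36 at n = 45. This is a guide only, since the mixed model's interval will differ.
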